The STOMP behavioral intervention consists of 12 intervention sessions (6 group and 6 individual sessions). The sessions will be completed over a period of 12-16 weeks from enrollment. The first intervention session will be a group session for all participants followed by individual and then alternating group and individual sessions for the rest of the intervention. The intervention group will utilize a study manual on pain management in which they will use with each session.

Group intervention Sessions

A total of 6 group sessions will be conducted over a period of 12-16 weeks from study enrollment date. These sessions will be led by a peer. A peer is an HIV-infected patient of the UAB or UNC clinics living with chronic pain and is a successful self-manager of his/her chronic pain. Peers will receive training that will include being a participant in all one-on-one sessions, and additional training to co-facilitate the six group sessions with the interventionist. Prior to the beginning of the first group session, participants will sign an Agreement of Confidentiality.

Participants will receive a reminder call/text approximately 48 hours before the group session to remind them of the upcoming session by the peer interventionist. If the participants cannot be reached on first contact, the peer interventionist will conduct up to three reminder calls or texts before the group session. Participants will also be notified of the upcoming group sessions at the end of each one-on-one intervention. Group sessions will be conducted in designated clinics at UAB and UNC. A sign-in sheet will be used to document attendance. Session notes will be used to document any major issues presented or any anecdotal nuances identified. The date, start time and end time of the

session will also be documented. Participants will complete an anonymous session feedback form at the end of each session. Each session will be audio recorded and transcribed later using a third party.

Individual Intervention Sessions

A total of 6 individual sessions will be conducted over a period of 12-16 weeks from study enrollment date.

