All participants in the intervention group will also receive a REDCAP assessment at baseline, post-intervention (0-month, after all sessions are completed), and then at 3, 6, 9 and 12 months post-intervention. The primary outcome will be at 3 months, and a 1-month window will be allowed after each timepoint for the patient to be contacted and assessed. An important medical event form will be administered to each participant at post-intervention (0-month) to screen for any unexpected medical incident, the severity of the event, its relation to the study, and medical follow-up. Viral load will also be

collected at baseline and at 12 months. At baseline, if a viral load from the prior 6 months is available in the medical record, that value will be recorded; otherwise, a viral load will be drawn. At 12 months, if a viral load in the prior 3 months is available in the medical record, that value will be recorded; otherwise, a viral load will be drawn. We will continue to conduct assessments every six months until the end of the study for all participants who complete the intervention by the beginning of Year 3. Participants who completed the baseline assessment by April 30, 2021 will continue to receive outcome assessments until April 2023 for a maximum of 41 months or 3 years. These assessments may be conducted by phone, if necessary, or in person. They will also participate in an audio-recorded in-person qualitative interview at the mid-point and end of the trial which will be transcribed using a third party company.

We will also investigate the intervention's impact on use of prescribed and non-prescribed opioids. Study staff will ask at each baseline and outcome assessment (0,3,6,9,12) the name of the participants' pharmacies along with the list of their current medications and dosage. Study staff will print out the medication lists and review it against the Opioid Medication Resource to identify the prescribed opioids. With written consent and a signed release of information from participants, a study staff member will contact the participants' pharmacy (or pharmacies) at the 12-month assessment to verify the self-reported information provided by the participants in the prior assessments. The data will be added into an excel spreadsheet for collection and analysis. Participants will receive up to 3 reminder calls at about a week and 48 hours prior to the next outcome assessment.

Qualitative interviews

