Participants assigned to intervention arm, peers and interventionists of the study will be interviewed at mid-point of the study and end of the study to provide their feedback on the STOMP intervention. These interviews will be audio-recorded and later transcribed using third party. Participants will be compensated \$50 for each of the qualitative interviews.

e) COMPARISON CONDITION

The comparison group will receive “treatment as usual” as described above. The comparison group will also be provided with the intervention manual, however, no additional treatment will be provided to participants allocated to the control group.

Assessments

The comparison group participants will complete the post-intervention (0-month) follow-up at the same timing of the intervention group (12 - 16 weeks) after the 1st intervention session., and then will complete the outcome assessments (3,6,9,12) as the intervention group as described above including the baseline and the 12-month viral load assessments, and the important medical event screening at post-intervention. We will continue to conduct assessments every six months until the end of the study for all participants who complete the baseline assessment by the beginning of Year 3. Participants who completed the baseline assessment by April 30, 2021 will continue to

receive outcome assessments until April 2023 for a maximum of 41 months or 3 years. These assessments may be conducted by phone, if necessary, or in person.

We will also investigate the intervention's impact on use of prescribed and non-prescribed opioids. Study staff will ask at each outcome assessment (3,6,9,12) the name of the participants' pharmacies along with the list of their current medications and dosage. Study staff will print out the medication lists and review it against the Opioid Medication Resource to identify the prescribed opioids. With written consent and a signed release of information from participants, a study staff member will contact the participants' pharmacy (or pharmacies) at the 12-month assessment to verify the self-reported information provided by the participants in the prior assessments. The data will be added into an excel spreadsheet for collection and analysis. Participants will receive up to 3 reminder calls at about a week and 48 hours prior to the next outcome assessment.

f) PEER INTERVENTIONISTS

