Sample Size Calculation. Our primary outcome is the BPI-Total score as described above. Given that 20 participants progress through the study at a time, our total sample size should be divisible by 20. A sample size of 210 will provide 85% power to detect a difference of 1 on a 10 point scale with at standard deviation of 2.4 assuming a two-sample t-test with equal variance. The IMMPACT guidelines suggest that a change of 1 on the BPI is a minimum clinically significant difference. Additionally, the difference we found in our pilot trial was 1 (SD=2.4). Therefore, a sample size of 210 is sufficient to detect this effect size. To become divisible by 20 and allow for 25% dropout (slightly more than in the pilot trial) we will recruit 280 participants. With our anticipated sample size, we will be able to estimate a margin-of-error of 1.5 percentage points for 95% intervals. For secondary outcomes, we can detect an effect size of 0.4, a medium effect, for continuous measures and a difference of proportions between 7.5% and 17% for binary measures, each with 85% power.

Interim & Final Analyses. We will not have any planned interim looks for stopping for efficacy, although safety and tolerability data will be monitored by the study DSMB at each meeting. The final analyses will be conducted once study follow-up is complete, after all data is

cleaned, and once the study database is locked. We anticipate database lock will happen by February 2024 with completion of primary analyses occurring by March of the same year.

Analysis Sets. The full analysis set will be based on an intention-to-treat (ITT) analysis with a per-protocol (PP) sensitivity analyses. The ITT analysis set will comprise all participants who have been randomized to either study arm, regardless of length of follow-up or actual intervention received.

Endpoint and Covariates

Our primary outcome will be the Brief Pain Inventory (BPI)-Total score, a commonly used composite measure of pain severity and the impact of pain on an individual's function. The BPI asks 11 questions about pain severity (pain at its worst, least, average, and right now) and the interference of pain in several aspects of patients' lives (activity, mood, walking ability, work, relations with other people, sleep, and enjoyment of life) on a scale of 0 (no pain/does not interfere) to 10 (pain as bad as you imagine/completely interferes). The BPI-Total score is the average score across all 11 questions.

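### The only visible scheduled screen for important medical events is at 0 months, so about 76-81% of follow-up to the 12-month visit falls after it in both arms

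*Combined protocol and SAP*

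**What the plan says.** Section III.d (Intervention, Assessments) sets the event screen for the intervention arm: "An important medical event form will be administered to each participant at post-intervention (0-month) to screen for any unexpected medical incident". Section III.e (Comparison Condition, Assessments) lists the same item for the comparison arm: "and the important medical event screening at post-intervention". Neither section names a later administration.

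The Assessment Table in III.l fits this. Section VII is the one row marked at 0 months alone, while Sections III to VI are marked at every visit from 0 months to the long-term assessments. The rows carry no labels, so matching Section VII to the event form is an inference. The timing rests on III.d and III.e and does not need it.

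On follow-up, section III.d says of the sessions: "The sessions will be completed over a period of 12-16 weeks from enrollment". The 0-month assessment comes next, "and then at 3, 6, 9 and 12 months post-intervention", and "a 1-month window will be allowed after each timepoint". Early enrollees go on with six-monthly assessments "for a maximum of 41 months or 3 years".

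On oversight, the SAP (Interim & Final Analyses) plans no efficacy look, "although safety and tolerability data will be monitored by the study DSMB at each meeting". It does not list the data that the DSMB receives.

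**The concern.** The plan looks for benefit after the sessions end. The SAP examines sustained differences at 3 months. The protocol follows opioid use through the 12-month assessment and collects viral load at 12 months. A balanced account of those months needs harm data collected in the same way in both arms.

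The one event question that the visible text puts to everyone is asked at the start of that period and not again. Events that surface later only through unsolicited reports depend on how much contact each arm has with staff. STOMP participants have far more of it during the programme, and by the end of it they know the staff better. Such reports do not support a fair comparison between arms, and a late imbalance could be missed or could be an artefact of reporting. In addition, a participant who misses the 0-month form has no later scheduled screen in the visible text.

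**Working it through.** The documents give no figure on this point, so there is none to reproduce.

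**Inputs**
- Event screen: once, at 0 months, in both arms (III.d, III.e).
- Time from enrolment to 0 months: w = 12 to 16 weeks (III.d).
- Later assessments: 3, 6, 9 and 12 months after the 0-month visit (III.d, III.e).
- Visit window: up to 1 month after each timepoint (III.d).
- Conversion: 12 months = 52 weeks, so 3 months = 13 weeks and 1 month = 52/12 = 4.33 weeks.

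**Formula.** Share of follow-up after the only screen = T / (T + w), where T is the time from 0 months to the visit in question.

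| Horizon | w = 12 weeks | w = 16 weeks |
|---|---|---|
| 3-month visit (T = 13) | 13/25 = 52% | 13/29 = 45% |
| 12-month visit (T = 52) | 52/64 = 81% | 52/68 = 76% |

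**Sensitivity to the window**
- Form given one month late, w = 16: (52 − 4.33)/68 = 70%.
- 12-month visit one month late, w = 12: (52 + 4.33)/(64 + 4.33) = 82%.

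**Long-term participants.** The text gives both 41 months and 3 years as the maximum, and these need to be reconciled.
- Lowest share: 36 months (156 weeks) counted from baseline, w = 16, gives (156 − 16)/156 = 90%.
- Highest share: 41 months (177.7 weeks) counted from 0 months, w = 12, gives 177.7/(177.7 + 12) = 94%.

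**Starting point of w.** III.d counts the 12 to 16 weeks from enrolment, while III.e counts them from the first intervention session. If the second applies, w from enrolment is longer and the shares are slightly lower.

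**Do the other visible routes fill the period after 0 months?**
- *Adverse event form* (III.d, Individual Intervention Sessions): completed when an issue arises from taking part and needs immediate attention. It is described within the STOMP session procedures.
- *Weekly team meetings* (III.k): adverse events are discussed, but nothing is asked of participants.
- *Crisis protocol* (VI): acts if danger or suffering becomes apparent during data collection. It has no limit by arm or visit, but it is triggered, not scheduled.
- *Medication lists* (III.d, III.e): scheduled in both arms at 3, 6, 9 and 12 months, but their stated use is to identify opioids.
- *CNICS abstraction* (III.i): viral load, CD4 count, co-morbid conditions, visit adherence and medications. Hospital admissions and overdoses are not named.
- *Mid-study call* (retention procedures, III.m): comparison arm only, 8 weeks after the intervention begins, to confirm contact details.

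None of these is a scheduled event question put to both arms after 0 months.

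**The case against.** A reader might infer that the DSMB gets no systematic safety data for most of follow-up. The documents do not support that. The SAP says "safety and tolerability data will be monitored by the study DSMB at each meeting" without listing the inputs, and the text after the heading of section VII, Protection of Human Subjects, is not in the copy reviewed. Reporting rules may stand there. The 76-81% is the share of time that the event form does not cover. It is not a share shown to lack safety data.

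A reader might also infer that no later form asks about events, or that later harm would go uncollected. Neither can be shown. The contents of Sections III to VI are not given, and III.m refers to an attachment for the assessments. The PHQ-8 is an outcome at 3 months, medication lists continue, and the crisis protocol applies during any data collection. These bear on depression and opioid use, though they are not event screens.

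On design, the 0-month form falls at the end of the sessions and so covers the period of delivery, and this is a behavioural programme. The SAP puts the primary endpoint immediately after the intervention and stops its sustained analysis at 3 months, so 45-52% is the relevant share for the SAP's own analyses. How often to screen afterwards is a design choice, and no passage contradicts another on it.

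These points limit the claim and hold its severity down. They do not remove it: no visible route gives comparable event data by arm after 0 months.

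**Conclusion.** The point holds as a gap in scheduled, comparable event collection. The visible plan screens both arms once for important medical events, at 0 months. About 76-81% of follow-up to the 12-month visit comes later (70-82% across the visit windows). So does about 45-52% of follow-up to the 3-month visit, the timepoint that III.d calls primary and the SAP uses for sustained effects. That difference over the primary timepoint needs reconciling in its own right. For participants followed longest, the share is about 90-94%.

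The shares assume 12 to 16 weeks from enrolment to the 0-month visit and that the visible schedule is complete for this form. No number of missed events is claimed, because the documents give no event rate. What the DSMB reviews after 0 months is unstated in the visible text. It is not shown to be nothing. This is an improvement the sponsor should make, not an error that invalidates the efficacy analysis.

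**What to change.** Amend III.d, III.e and the III.l table so that the existing important medical event form is given in both arms at the 3-, 6-, 9- and 12-month assessments and at each long-term assessment, in person or by phone. Each form should cover the period since the last completed one, so that a missed form, including the one at 0 months, is made good at the next visit. In the SAP, state that the DSMB receives cumulative counts by arm from this form.

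If all forms are completed, each participant has 5 screens to 12 months instead of 1, and the uncovered share to that visit falls from 76-81% to 0%. CNICS abstraction should not be counted on as a back-up, because the items listed in III.i do not name such events.

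The cost is a protocol amendment, a few more minutes per visit and more event reports to process. The visits are already scheduled and paid (III.n), and the protocol already provides for assessment by phone. The change concerns data collection only and leaves clinical management untouched.

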Comprehension will be assessed by asking the participant to summarize the study activities or some general open ended questions will be asked like what can you tell me about this study, can you tell me about how long the study may last, etc. The consent process is estimated to take around 30 minutes. Study staff will ensure that the participant has signed and dated the consent form including the HIPAA form. All signed consent forms will be stored in locked file cabinets under respective participant files.

Baseline Assessment

The research staff will then administer the baseline assessment which includes a confirmatory set of screening questions via RedCap. Confirmation of the participant's eligibility will be recorded in RedCap. If a participant is ineligible based on this RedCap assessment, they will be given a \$50 incentive and thanked for their time, and they will

not be considered to have been enrolled in the study at any point (informed consent is asked before this point so that we can use any data generated in published findings). If a participant is eligible, they will also be thanked for coming and given their \$50 incentive payment for their time. Completion of Baseline assessment will be recorded in excel logs.

RANDOMIZATION

Our team will utilize a 1:1 ratio for allocation to the STOMP intervention and Usual Care (UC) conditions. Our study statistician, [name], will use SAS to generate the randomization scheme stratified by whether the participant is on long-term opioid therapy (taking prescribed opioids for at least 3 months) and whether they have chronic multisite pain (pain in at least 3 locations or pain all over). Importantly, the PIs and outcomes assessors will be blinded to intervention vs. comparison allocation. Participants in the intervention and comparison conditions will have full access to all available clinical services at their respective sites.

d) INTERVENTION

The intervention group will receive “treatment as usual” plus the STOMP behavioral intervention. The “treatment as usual” refers to the standard of care that patients receive at the UAB and UNC clinics. This standard of care is for patients to discuss chronic pain with their providers at their discretion. Although highly variable, providers can recommend and prescribe pharmacologic (e.g., opioid and other pain medication), non-pharmacologic (e.g., physical therapy, referral to psychology) approaches for pain. This study will not interfere in any way with usual care.

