We will use a structured fidelity assessment tool developed by the study PI and psychologist consultant [name]. To assess one-on-one session fidelity across interventionists, time, and sites, we will audio record sessions. Initially, we will listen to and rate all one-on-one sessions. Once an interventionist completes five consecutive sessions with 80% fidelity, we will "certify" the interventionist as having the competence necessary to continue to conduct the intervention. Thereafter, a blinded assessor with intervention delivery experience trained by [name] will review a 10% random sample. We will also provide ongoing supervision to prevent interventionist drift. We will monitor treatment receipt by using a checklist, which will capture whether

participants have used their tracking logs (which will be photocopied at each session by the staff interventionists). Given the less structured format of the group sessions, they will be assessed for knowledge sharing between the peers and participants and among participants, reflection on one-on-one session content, and fostering social support.

h) COLLECTION OF COST DATA

Each site will be responsible for tracking the following items in real-time: up-front training hours, cost of snacks, travel vouchers and participant manuals. Individual and group sessions will be tracked using the audio-record capability.

i) COLLECTION OF CNICS DATA

Center for AIDS Research Network of Integrated Clinical Systems (CNICS) Data:
CNICS data will be collected from abstractions from site medical record databases in collaboration with the CNICS data collection and patient reported outcomes infrastructure. Clinical and medical history data will include HIV viral load, CD4+ T-cell counts, co-morbid conditions, HIV primary care visit adherence, and medications. HIV primary care visit adherence will be extracted on all HIV care visits from the date of enrollment until the end of the study. Data from CNICS Patient Reported Outcomes (PRO) questionnaires including assessments of pain will be identified by study code and managed in accordance with CNICS electronic storage and data transfer guidelines.

j) TRACKING OF STUDY PATIENTS

Study staff will use the study's RedCap database to capture reminder calls, study visits, assessments, and intervention activities. Study staff will use excel logs to capture

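### The comparison arm's medication query leaves out the 0-month visit listed for STOMP, and the long-term follow-up rule differs between sections: two minor inconsistencies to reconcile

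*Combined protocol and SAP*

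**What the plan says.** **Medication query.** For STOMP, protocol III.d (Assessments) states "Study staff will ask at each baseline and outcome assessment (0,3,6,9,12) the name of the" participant's pharmacies, together with current medicines and doses. For the comparison arm, the matching paragraph of III.e reads "Study staff will ask at each outcome assessment (3,6,9,12) the name of the" same items. Both paragraphs give the purpose as studying the intervention's "impact on use of prescribed and non-prescribed opioids". Both send staff to the pharmacies at 12 months "to verify the self-reported information provided by the participants in the prior assessments".

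The comparison arm does have the visit: "The comparison group participants will complete the post-intervention (0-month) follow-up at the same timing of the intervention group". The same sentence goes on to say that this arm will "complete the outcome assessments (3,6,9,12) as the intervention group as described above", naming viral load and the medical event screen as included. It does not name the medication query.

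**Long-term follow-up.** III.d continues six-monthly assessments for those who finish the intervention by the start of Year 3. III.e continues them for those who have a baseline assessment by that time. The REDCap row of III.m, which is not limited to one arm, uses finishing the intervention. III.d and III.e each add the same dated rule: participants with baseline by April 30, 2021 are followed until April 2023. Both give the maximum as 41 months and also as 3 years. No section dates Year 3 or ranks the rules.

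**The concern.** The two medication paragraphs are otherwise almost identical, and their stated purpose is a comparison between arms. If site staff follow the text, opioid self-report at 0 months exists for STOMP only. That time point could then not be compared using the query, and the 12-month pharmacy contact would have no comparison-arm report from 0 months to verify.

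For long-term follow-up, finishing the intervention is a post-randomisation event that only STOMP participants can literally experience. Selecting STOMP on that event and controls on baseline would compare a group selected for completing treatment with an unselected one. At stake is the validity of any long-term between-arm comparison, should one be made.

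**Working it through.** No stated figure is in dispute, so the check sets the sections side by side.

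**Medication query**

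- STOMP (III.d): baseline and {0, 3, 6, 9, 12}, so 5 post-baseline queries.
- Comparison (III.e): {3, 6, 9, 12}, so 4 post-baseline queries.
- Difference: {0, 3, 6, 9, 12} minus {3, 6, 9, 12} = {0}. One follow-up query is unlisted, at a visit that takes place.
- Baseline is also absent from the III.e list. This has little practical weight, because III.c places the baseline assessment before randomisation, when arm is not yet known.

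Planned number of reports involved:

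- The SAP (Sample Size Calculation) plans 280 participants with 25% dropout, from 210 / (1 − 0.25) = 280. The plan's own figure reproduces.
- Protocol III.c (Randomization) says "Our team will utilize a 1:1 ratio for allocation", so the comparison arm is 280 / 2 = 140.
- After dropout: 140 × 0.75 = 105.

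**Does other text settle it?**

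- The cross-reference to the intervention arm in III.e is attached to the 3, 6, 9, 12 list, so it does not add 0 months.
- The assessment table (III.l) makes no distinction between arms and marks 0 months, but it shows only section numbers. It does not show where the medication query sits.
- III.i abstracts "co-morbid conditions, HIV primary care visit adherence, and medications" from clinic records in both arms. This may partly cover prescribed opioids, but no 0-month timing is given for medications, and it is not the self-report that the pharmacy contact verifies.

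**Long-term rule**

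| Section | Year 3 rule: qualifying event | April 30, 2021 baseline rule |
|---|---|---|
| III.d (STOMP) | finishing the intervention | yes |
| III.e (comparison) | completing baseline | yes |
| III.m (arm not specified) | finishing the intervention | not stated |

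- If the Year 3 rule is applied as worded in III.d and III.e, the STOMP cohort depends on a post-randomisation event and the comparison cohort does not. With the same cutoff, the two events lie 12 to 16 weeks apart (III.d): 12 × 7 / 30.4375 = 2.8 months to 16 × 7 / 30.4375 = 3.7 months.
- If the dated rule governs, both arms are selected on baseline date and the difference is 0.
- The number of participants affected cannot be computed, because Year 3 is undated and no session-completion rate is given.
- Maximum duration: 3 years = 36 months, and 41 − 36 = 5 months apart. November 2019 (the protocol date) plus 41 months is April 2023, and 41 is the last long-term visit for both arms in III.n. This fits the dated rule, but only if follow-up is counted from the protocol date, which no section states.

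**The case against.** The strongest reply is that the 0-month omission is a slip with little at stake. III.e mentions the 0-month follow-up separately and then uses 3, 6, 9, 12 as its label for outcome assessments; the query sentence may simply repeat that label. Elsewhere the arms share a schedule: III.l does not split them, the reminder-call row of III.m includes 0, and the control payment list in III.n includes 0. Opioid use is not among the three aims in protocol II, and the SAP lists no opioid outcome. All of this stands. It lowers the weight of the point, but it does not make the two lists agree.

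On long-term follow-up, the reply is that the dated rule is the same in both arms, III.n lists the same long-term visits for both, and finishing the intervention may be meant only as a time marker. III.d also foresees participants who stop sessions but still complete outcome assessments, which weighs against making follow-up depend on attendance. These are reasonable readings, but no section adopts one.

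A reader might infer more than the documents support:

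- That the arms were deliberately measured differently. Nothing indicates intent.
- That comparison participants were in fact not asked at 0 months. The protocol shows what was written, not what was done.
- That the primary result is biased. The SAP analyses use pain and related scales at 0 and 3 months, and neither inconsistency touches them.
- That long-term STOMP follow-up was in fact restricted to completers. That follows only if the Year 3 rule was the one applied.

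**Conclusion.** Both inconsistencies are real, and both are minor.

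For the medication query, one of five post-baseline time points is unlisted in the comparison arm, covering 140 planned reports or 105 after the planned dropout. Those counts assume the planned enrolment, equal arms, dropout at the planned rate in the comparison arm, and literal adherence to III.e. The loss is one time point of an exploratory measure for which the SAP sets out no analysis, and clinic-record abstraction may cover part of it.

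For long-term follow-up, the size ranges from none (dated rule governs) to an amount the documents do not allow one to calculate (Year 3 rule applied). Neither the protocol nor the SAP specifies a long-term between-arm analysis, so it matters only if one is carried out.

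**What to change.** **Medication query.** In III.e, list the query at baseline and 0, 3, 6, 9 and 12 months, as in III.d. If the visits have passed, check the records to see whether comparison participants were asked at 0 months. If they were, keep the data and correct the text. Limit the query-based between-arm comparison to 3 months onward only if the data are absent, and say so in the report.

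**Long-term follow-up.** Reconcile III.d, III.e and III.m to one rule for both arms based on the date of the baseline assessment, without the condition on finishing the intervention, and state one maximum duration. If follow-up is over, report which rule was applied in each arm. Restrict any long-term between-arm comparison to participants with baseline by the same date in both arms, regardless of session completion, and count those not followed as missing.

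**Cost.** A short wording amendment. The query adds perhaps a few minutes at a visit that already takes place. Long-term follow-up costs at most 5 visits (18, 24, 30, 36 and 41 months in III.n) × $50 = $250 in payments per STOMP participant who would otherwise be left out, plus staff time. If all visits have passed, the cost is a records check, a reporting note and, where needed, a restricted analysis set.
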